#### CONFIDENTIAL

- Pooled analysis of 11 randomised artemether-lumefantrine (Coartem) studies [Mueller, 2006]: PCR-corrected rate (Per Protocol population) = 97%
- Open-label study of artesunate-amodiaquine [Oyakhirome, 2007]: PCR-corrected rate (PP population) = 86%
- Randomised open-label study of artesunate-SP, artesunate-amodiaquine and artemether-lumefantrine (Coartem) [van den Broek, 2006]: PCR-corrected rates (PP population) =
  - 90% (artesunate-SP)
  - 98.5% (artesunate-amodiaquine)
  - 100% (artemether-lumefantrine)
- Open-label randomised study of artesunate-SP and artesunate-amodiaquine, [Hamour, 2005]: PCR-corrected rates (PP population) =
  - 91% (artesunate-SP)
  - 93% (artesunate-amodiaquine)

The published 28-day parasitological cure rates range from 86% to 100%, although differences in study design, methodology and analysis could account for this wide range of observed effects. However, within the Van den Broek study of 298 patients, the effects of three different anti-malarial combinations ranged from 90% to 100%. Therefore, the choice of a 7% margin is still considered to be appropriate for this study.

#### 11.2.2. Sample Size Assumptions

A total of 650 evaluable patients in the CDA group and 325 evaluable patients in the artemether-lumefantrine group will provide **at least** 90% power to show non-inferiority of CDA to artemether-lumefantrine in terms of a one-sided hypothesis test with a 2.5% significance level for the primary endpoint of the parasitological cure rate at Day 28 (PCR corrected). This is based on using a 7% non-inferiority margin and a 2:1 allocation ratio, assuming 93% efficacy for CDA and 95% efficacy for artemether-lumefantrine amongst patients evaluable for the primary per-protocol population.

A 2:1 ratio has been chosen to preferentially collect information on the combination of CDA to artemether-lumefantrine, due to an interest in collecting additional safety data on the CDA arm.

In order to accommodate up to 30% loss of evaluable data due to missing data where patients are lost to follow-up, or have been lost to analysis due to retreatment for a new infection, it is planned that a total of 1395 patients will be enrolled (930 to CDA, 465 to artemether-lumefantrine).

At the time of sample size calculation for this study, the Day 28 PCR corrected Parasitological Cure Rate of artemether-lumefantrine was estimated to be 95% with values in the literature ranging between 93.5% to 97.5%. These parasitological cure rates have been observed in different trials run in different regions of the world at different times and in different populations.

It is expected that the efficacy rate for CDA will similarly be 95% (ie. a 0% treatment difference). However, due to the lack of data for CDA, a more conservative treatment difference is being used to calculate the sample size with 95% for artemether-lumefantrine and 93% for CDA (ie. a 2% treatment difference).

The impact on the power of the study due to deviations from assumed response rates is discussed in Section 11.2.3.

A single primary endpoint analysis has been defined for this study with a single treatment comparison. No adjustments for multiplicity are therefore required.

# 11.2.3. Sample Size Sensitivity

The robustness and sensitivity of the above sample size should be considered in order to assess the impact of different circumstances on the power of the per-protocol analysis for the primary endpoint.

Power will vary if the observed parasitological cure rate at day 28 for artemetherlumefantrine is different to the expected 95%. As stated in Section 11.2.1, published values from trials run in different regions of the world at different times and in different populations, range from 93.5% to 97.5%. The data presented shows for different scenarios how the power of the analysis decreases if the parasitological cure rate at day 28 increases above 95%, within this observed range:

# Table 1Variation in power with different artemether-lumefantrine
parasitological cure rates

Observed CDA rate:	Artemether-lumefantrine rate						
93.1% (605/650)	95.1%	95.7%	96.3%	96.9%			
	(309/325)	(311/325)	(313/325)	(315/325)			
Power 	90.6%	84.3%	75.4%	63.2%			

1. Given a one-sided hypothesis at 2.5% significance level, a 7% non-inferiority margin, 650 evaluable CDA subjects and 325 evaluable artemether-lumefantrine subjects

Also as stated in Section 11.2.1, although it is expected that the efficacy rate for CDA will also be 95%, due a lack of available data for day 28, a conservative rate of 93% has been assumed. The data presented shows for different scenarios how the power of the analysis varies if the rate for CDA varies between 92% and 95%:

#### Table 2 Variation in power with different CDA parasitological cure rates

Observed artemether-	CDA rate	CDA rate						
lumefantrine rate: 95.1% (309/325)	92.0% (598/650)	92.5% (601/650)	93.5% 94.0% (608/650) (611/650)					
Power	70.8%	80.8%	95.1%	97.7%				

The impact on the power of the per-protocol analysis of observing a higher drop out rate than the assumed 30% of subjects enrolled, is considered below. This would result in there being fewer than the 650 CDA and 325 evaluable artemether-lumefantrine subjects available for the analysis to have 90% power, even if other sample-size assumptions are met:

Table 3	Impact of a higher drop out rate on the power of the study
---------	--

	CDA	Artemether-	Power
		lumefantrine	
Number of subjects enrolled:	930	465	
No. evaluable (% dropouts)	605 (34.9%)	305 (35.1%)	
Parasitological cure rate at Day 28	93.1%	95.1% (290/305)	88.3%
	(563/605)		

Thus there is only a small loss of power for the primary analysis if a 35% withdrawal/non-evaluability rate is observed (rather than 30%) but other assumptions for CDA and artemether-lumefantrine are met.

# 11.2.4. Sample Size Re-estimation

No sample size re-estimation is planned in this study.

# 11.3. Data Analysis Considerations

# 11.3.1. Analysis Populations

The following populations will be evaluated:

- Intent to treat
- Per Protocol
- Pharmacokinetic population

# Intent-to-treat population (ITT)

All subjects who were randomised and have received any dose of the study medication, irrespective of whether they vomited, will be included in the intent-to-treat population. The intent-to-treat analysis of efficacy will be a supportive analysis population for the primary efficacy endpoint and will also be used for all secondary efficacy and safety analyses.

# Per-protocol populations (PP)

The Per Protocol (PP) population will consist of all subjects in the ITT population not identified as major protocol violators. The major protocol violations for which patients would be excluded from the PP population will be described in the Reporting and Analysis Plan and will represent violations that may impact the efficacy endpoints for

which non-inferiority comparisons are being made. The decision to exclude a subject from the PP population will be made prior to breaking the blind. This population will be used for primary analysis of the day 28 cure rate and supportive analysis of the secondary efficacy endpoints,

# 11.3.2. Analysis Data Sets

Data sets will contain a flag to identify for which analysis populations subjects are eligible. Additionally, modified population datasets will be created for the purposes of sensitivity analyses. Full details of these analysis datasets will be given in the Reporting Analysis Plan.

# 11.3.3. Treatment Comparisons

# 11.3.3.1. Primary Comparisons of Interest

The primary comparison of interest will be in the parasitological cure rate at Day 28 (PCR corrected) for artemether-lumefantrine versus CDA using the Day 28 Per Protocol Population.

The comparison will be made for CDA minus artemether-lumefantrine and a two-sided 95% confidence interval for the treatment difference will be used, giving a nominal significance level for falsely rejecting the null hypothesis of 2.5%. As only one comparison is being studied, no adjustment for multiple comparisons is required. Non-inferiority will be concluded if the lower bound of the two-sided 95% confidence interval is no less than than -7%.

# 11.3.3.2. Other Comparisons of Interest

A key supportive analysis using the Intent-to-Treat population will also be conducted as well as other sensitivity analyses to confirm consistency of the primary analysis results under varied assumptions or methods. (No adjustments are made for these sensitivity analyses).

Comparisons of CDA and artemether-lumefantrine may be provided for other secondary endpoints for descriptive purposes.

# 11.3.4. Interim Analysis

Interim analyses of efficacy and safety data are planned as follows:

- 1. An Independent Data Monitoring Committee (IDMC) is planned to review the risk:benefit ratio of CDA, and to achieve this will monitor both efficacy and safety aspects of this study. The details of the frequency and type of analyses will be described in the IDMC Charter.
- 2. An internal Safety Review Team (SRT) is planned to review the safety data on an ongoing basis. These reviews will be conducted while blinded to treatment details.

# 11.3.5. Key Elements of Analysis Plan

# 11.3.5.1. Data derivation

For the primary endpoint, Parasitological Cure Rate at Day 28, in order to be classified as 'cured' at Day 28, subjects must demonstrate parasite clearance of their initial infection either at day 7 (+/- 1 day) if tested at this time point, or earlier (during day 3 to 6) if not tested at day 7, and must remain clear of their initial infection at day 28 (- 1, +3 days) following PCR-correction. These are the minimum data points required for a subject to be included in the primary analysis.

If a positive parasite count is detected at any intermittent timepoint day 7 to day 28, the patient will be programmatically classified as a 'failure'.

However, PCR analysis will be conducted on samples with positive counts at any intermittent timepoint day 7 to day 28 to assess if the parasites represent a recrudescence (re-infestation of the original baseline parasite infection) or a re-infection (infection with a new parasite after the baseline assessment). If a positive parasite count is determined to be a re-infection then the data for this subject will not be included as a 'failure' but rather will be excluded from the analysis since a new infection does not demonstrate a failure to treat the original infection.

Similarly, for the Day 14 analyses, patients must have data at either day 7 (+/-1 day) if tested at this timepoint or earlier (day 3 to 6) if not tested at day 7, and must remain clear of their initial infection at day 14 (-1,+3days) following PCR-correction. These are the minimum data points required for a subject to be classified as a responder in the Day 14 analyses. The Day 42 analysis would require the same timepoints; however, instead of Day 14 (-1,+3 days), Day 42 (-1,+3 days) would be required.

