## 3. ENDPOINT(S)

## 3.1. Primary

#### Primary Efficacy Endpoint:

• Parasitological cure rate, PCR-corrected, at day 28, in the per-protocol population. Parasitological cure rate is defined as the clearance of the initial malaria infection by day 7 and remaining free of this infection to the day of assessment (PCR of the parasite genotype is used to distinguish between a new malaria infection and a reappearance of the initial infection (recrudescence)). The intent-to-treat population is a key supportive analysis.

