#### 6.3.2. Parasite DNA analysis

Two drops of peripheral blood will be collected onto pre-printed filter papers, for subsequent DNA extraction and PCR analysis of *P.falciparum* DNA, on all subjects at screening and any day on or after day 7 when a blood slide is prepared.

PCR of the *P.falciparum* genes MSP-1, MSP-2 and GLURP will be used to distinguish between the initial infection reappearing (recrudescence or inadequate therapy received) and a new infection occurring on any day on or after day 7 in the 42-day follow-up period.

Resistance marker work will investigate the presence of mutations associated with resistance of anti-folate drugs in the genes encoding DHFR and DHPS [Kublin, 2002] and resistance to lumefantrine, *Pf*mdr gene, as below. DNA extraction from the dried filter-paper blood spots and mutation-specific nested PCR and /or restriction digestions to detect these mutations will be performed at a single laboratory, see Study Reference Manual for further details.

DHFR codons 51, 59, 108 and 164; DHPS codons 437, 540, 581 and 613; *Pf*mdr186N

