# 11.3.5.2. Missing data

For the ITT population, subjects will not be excluded from any statistical analyses with the exception of efficacy analyses for PCR-confirmed cases of new malarial infection. For the primary endpoint for this population, an imputation of treatment failure will be made for subjects without a day 28 parasitological assessment. However, all data summaries of the ITT population will be performed with no replacement of missing CRF efficacy and safety data. Patients with missing data at the relevant timepoint will be excluded from analyses for the Per Protocol population eg patients withdrawing from the study prior to day 28 will be excluded from the primary endpoint analysis for the Per Protocol population. Full details of how missing CRF data will be handled will be described in the Reporting Analysis Plan.

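### The PCR exclusion for re-infection starts at Day 7 without any documented clearance, so a child positive on every slide from Day 3 through Day 7 can be dropped from both PP and ITT instead of counting as a failure

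*Protocol*

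**What the plan says.** - **Endpoint (section 3.1).** Parasitological cure is "clearance of the initial malaria infection by day 7 and remaining free of this infection to the day of assessment". PCR is there to tell a new infection from a return of the original one.
- **Derivation (section 11.3.5.1).** To be classed as cured, "subjects must demonstrate parasite clearance of their initial infection either at day 7 (+/- 1 day) if tested at this time point", or between Day 3 and Day 6 if there is no Day 7 test. A positive count from Day 7 to Day 28 is a failure by default. However, "PCR analysis will be conducted on samples with positive counts at any intermittent timepoint day 7 to day 28 to assess" whether the parasites are recrudescent or new. If new: "If a positive parasite count is determined to be a re-infection then the data for this subject will not be included as a" failure, and the child is excluded from the analysis.
- **PCR window (section 6.3.2).** PCR separates the original infection from "a new infection occurring on any day on or after day 7 in the 42-day follow-up period". The first day on which a new infection can be called is thus also the clearance deadline.
- **PCR outcomes (section 6.3.3).** Recrudescent and inconclusive results are failures.
- **Evaluability (section 11.3.5.3).** An early slide must be recorded. It need not be negative.
- **ITT (section 11.3.5.2).** Nobody is excluded, "with the exception of efficacy analyses for PCR-confirmed cases of new malarial infection".
- **Sensitivity analysis (section 11.3.5.7).** A PP analysis of the Day 28 cure rate without PCR correction is planned.

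**The concern.** The endpoint has two steps: clear the initial infection by Day 7, then stay free of it. The Day 7 slide tests the first step. Section 11.3.5.1 also sends a positive Day 7 slide to PCR, and a genotype read as new removes the child before the first step has been judged. The stated reason for exclusion is that a new infection does not show failure to treat the original one. That reason is sound for a child seen to clear. It is not established for a child with no negative slide in the clearance window, for whom the only evidence that the original infection has gone is the genotype call itself.

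Removing such children takes failures out of the denominator and raises the observed cure rate. If this happens more often on CDA, the bias favours non-inferiority, and the key supportive ITT analysis gives no protection because it applies the same exclusion.

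**Working it through.** **1. Tracing one child through the rules.** Positive on the Day 3 slide, positive at the Day 7 visit, Day 7 genotype read as new.
- Section 11.3.5.3: early slide recorded. The child can be evaluable.
- Section 11.3.5.1, cured: no clearance shown. Not cured.
- Section 11.3.5.1, default: positive from Day 7. Failure.
- Section 11.3.5.1, PCR step: typed new. Failure withdrawn, child excluded.
- Section 6.3.3: neither recrudescent nor inconclusive, so it does not restore the failure.
- Section 11.3.5.2: excluded from ITT efficacy as well.
- Section 6.3.4: the early-treatment-failure criteria may catch some of these children, but they define ACPR, a secondary endpoint, and do not enter the primary classification.

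**2. Checking the design inputs (section 11.2.2).** 650 and 325 evaluable, 93% v 95%, margin 7%, one-sided 2.5%. Power with unpooled Wald variance is 89.0%; with restricted-MLE (Farrington-Manning) variance it is 90.2%. The stated figure of at least 90% is reproduced by the second method, so these inputs can be used below.

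**3. Effect on type I error.** The protocol gives no frequency, so v (CDA) and w (comparator) are assumed shares of children never cleared, and q is the assumed share of those typed new. Take true rates at the margin: 0.88 v 0.95.

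Observed rates: a = 0.88/(1 − vq), b = 0.95/(1 − wq). Sample sizes: 650(1 − vq) and 325(1 − wq). Error = Φ[(a − b + 0.07)/SE − 1.96], with unpooled SE.

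Worked case, v = 1%, w = 0.5%, q = 0.5: a = 0.88/0.995 = 0.8844; b = 0.95/0.9975 = 0.9524; difference −6.80 points; SE = 0.01726; Φ(0.00204/0.01726 − 1.96) = Φ(−1.84) = 3.3%. This corresponds to about 3 CDA children (650 × 0.005 = 3.25) and 1 comparator child (325 × 0.0025 = 0.8) deleted.

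| v (CDA) | w (comparator) | q | Difference (points) | Type I error |
|---|---|---|---|---|
| 0 | 0 | – | −7.00 | 2.5% |
| 0.5% | 0.25% | 0.25 | −6.95 | 2.7% |
| 1% | 0.5% | 0.5 | −6.80 | 3.3% |
| 2% | 0.5% | 0.5 | −6.35 | 5.7% |
| 1% | 1% | 0.5 | −7.04 | 2.4% |
| 2% | 2% | 0.5 | −7.07 | 2.3% |

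The last two rows are the equal-deletion case: error falls slightly.

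**4. How few children could matter near the margin (illustration).** Comparator 309/325 and CDA 592/650: difference −4.00 points, lower 95% limit −7.21%, non-inferiority not shown. Delete two CDA failures, giving 592/648: difference −3.72 points, lower limit −6.91%, non-inferiority shown.

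**The case against.** The strongest reply is that the protocol speaks of clearing the initial infection, not of slide negativity. If the Day 7 genotype is truly new, the initial infection has gone, and counting the child as a failure changes the endpoint. Section 6.3.2 expressly allows a new infection to be called on Day 7, and its failure side includes inadequate therapy, so PCR is not plainly confined to interrupted parasitaemia. Persisting original parasites should match baseline and count as failures. Wrongful deletion therefore needs a mistyped sample, for example a clone missed in the baseline spot.

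Much of this stands. It makes the case rare, and it means the rule leaves a gap and does not flatly contradict the endpoint. It does not close the gap, because section 11.3.5.1 asks that clearance be demonstrated.

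A reader might infer that these children have one unbroken parasitaemia. The documents do not support that: no slide is scheduled between Day 3 and Day 7, and the home visits on Days 4 to 6 list none, so clearance in between would go unseen.

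A reader might also infer that the rule inflates type I error in this trial. That needs more deletion on CDA than on the comparator. No figure in the protocol supports such an imbalance, and section 1.2 notes that artesunate and artemether share an active metabolite.

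The PP analysis without PCR correction is a partial safeguard. It counts these children as failures, but it also counts every genuine new infection, so it gives a bound and cannot isolate the effect.

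Section 11.3.2 leaves dataset details to the Reporting and Analysis Plan. The exclusion rule, however, is already fixed in section 11.3.5.1.

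**Conclusion.** The point holds as a gap in the derivation rule. PCR can exclude a child as a re-infection from Day 7 with no documented clearance, in both the primary PP and the key supportive ITT analysis. Its size is unknown and probably small. Under assumed excess non-clearance on CDA, type I error goes from 2.5% to between 2.7% and 5.7%; with equal deletion in both arms it stays at or below 2.5%. These figures rest on assumed frequencies and on a true deficit exactly at the margin. They show sensitivity, not a demonstrated bias. The rule is still worth closing before unblinding, because a handful of children can decide a result near −7% and a choice made afterwards would be open to challenge.

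**What to change.** In section 11.3.5.1, carried into section 11.3.5.2, state that PCR may reclassify a positive slide as a re-infection only if the child had at least one asexual-negative slide within the clearance window (Day 3 to the Day 7 ±1 visit) before that positive slide. A child whose slides in that window are all positive, including the Day 7 visit, is a failure whatever the genotype, in PP and ITT. The negative slide should be tied to this window: accepting any negative slide after dosing would let a single early negative, followed by positives on Day 3 and Day 7, reopen the gap.

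The cost is one sentence and one programming condition on slides already collected, with no change to visits, planned sample size or treatment. The downside is that a rare child who cleared unseen between Day 3 and Day 7 and was then newly infected counts as a failure. Within either arm this can only lower the cure rate; the ruling is conservative for non-inferiority when it falls on CDA, and little changes if it falls equally on both arms.

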# 11.3.5.2. Missing data

For the ITT population, subjects will not be excluded from any statistical analyses with the exception of efficacy analyses for PCR-confirmed cases of new malarial infection. For the primary endpoint for this population, an imputation of treatment failure will be made for subjects without a day 28 parasitological assessment. However, all data summaries of the ITT population will be performed with no replacement of missing CRF efficacy and safety data. Patients with missing data at the relevant timepoint will be excluded from analyses for the Per Protocol population eg patients withdrawing from the study prior to day 28 will be excluded from the primary endpoint analysis for the Per Protocol population. Full details of how missing CRF data will be handled will be described in the Reporting Analysis Plan.

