## 3.2. Secondary

#### Secondary Efficacy Endpoints:

- Parasitological cure rate, PCR-corrected, at day 14 and 42, by treatment group.
- ACPR, and ACPR PCR corrected at day 14, 28 and 42, by treatment group.
- Summary of asexual parasite densities on days 0, 1, 2, 3, 7, 14, 28 and 42 by treatment group.
- PCT by treatment group.
- FCT by treatment group.
- Summary of gametocyte densities on days 0, 1, 2, 3, 7, 14, 28 and 42 by treatment group.

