#### 6.3.5. Clearance times (PCT and FCT)

Subjects will also be assessed for these secondary endpoints against the following definitions:

- **PCT**: Time needed to clear asexual parasite forms from the blood, parasite numbers fall below the limit of detection in a thick blood smear and remain undetectable for at least 48 hours.
- **FCT:** Time from the first dose of treatment to the time when body temperature falls to normal and remains so for at least 48 hours.

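### The ITT exclusion of PCR-confirmed new infections has no endpoint or time limit, so a late reinfection removes earlier, complete efficacy data

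*Protocol*

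**What the plan says.** Protocol section 11.3.5.2 (Missing data) gives one exception to ITT inclusion: "subjects will not be excluded from any statistical analyses with the exception of efficacy analyses for PCR-confirmed cases of new malarial infection". Section 11.3.1 makes the rule broad, because the ITT population "will also be used for all secondary efficacy and safety analyses".

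The relevant time windows are set elsewhere:

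- Section 6.3.2 uses PCR to separate recrudescence from "a new infection occurring on any day on or after day 7 in the 42-day follow-up period".
- Section 11.3.5.1, for the primary endpoint, is narrower: "PCR analysis will be conducted on samples with positive counts at any intermittent timepoint day 7 to day 28". A patient whose positive count proves to be a re-infection is then left out of that analysis.
- The same section requires for Day 14 that patients "must remain clear of their initial infection at day 14". Nothing after the Day 14 window is needed.
- Section 6.3.5 defines parasite clearance time (PCT) by counts that fall below detection and "remain undetectable for at least 48 hours". Fever clearance time (FCT) is "Time from the first dose of treatment to the time when body temperature falls to normal and remains so for at least 48 hours".

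Section 3.2 and the Protocol Summary promise two versions of one secondary endpoint: "ACPR, and ACPR PCR corrected at day 14, 28 and 42, by treatment group". Section 11.3.5.7 then lists ACPR at the same days with every version PCR-corrected.

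**The concern.** Membership of an ITT analysis should not depend on something that happens after the outcome has been observed. Under section 11.3.5.2 as worded, it does: whether a child's clearance time from the first days counts depends on whether a new infection is found weeks later.

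Three things are at stake.

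- Complete data on PCT, FCT, early densities and Day 14 cure are lost.
- The loss depends on a post-randomisation event that may differ by arm, so the comparison can lose its randomised balance. Section 1.2 gives lumefantrine a half-life of 5 to 10 days in patients. The protocol gives no half-life for chlorproguanil or dapsone, so neither the size nor the direction of an arm difference can be derived from it.
- Late exclusion removes mainly Day 28 successes from the key supportive ITT analysis, because a patient who is cured at Day 28 and then newly infected is a success at Day 28.

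New infections are also what separates uncorrected from corrected ACPR. If those patients are deleted, the two versions cannot differ in any useful way.

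**Working it through.** **1. Time windows side by side**

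| Analysis | Data it needs | New infection that can remove the patient under 11.3.5.2 |
|---|---|---|
| PCT, FCT | 8-hourly readings to Day 3, plus a 48-hour hold | Day 7 to 42 |
| Day 14 cure | To Day 14 (-1, +3) | Day 7 to 42 |
| Day 28 cure, ITT | To Day 28 (-1, +3) | Day 7 to 42 under 11.3.5.2; Day 7 to 28 under 11.3.5.1 |

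For a child who clears by discharge on Day 3, the hold ends by Day 3 + 2 = Day 5. That is before Day 7, the first day on which a new infection can be identified. No new infection can therefore invalidate that clearance time.

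**2. The plan's own figures**

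Power, by the normal approximation with unpooled variance (93% v 95%, 650:325, margin 7%, one-sided 2.5%):

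- SE = √(0.93×0.07/650 + 0.95×0.05/325) = 0.0157
- Power = Φ[(0.07 − 0.02)/0.0157 − 1.96] = 89.0%

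With the Table 1 counts (605/650 and 309/325) the result is 89.4%, against 90.6% stated. Enrolment is 975/0.70 = 1393, against 1395 stated. Both are close. The 30% allowance in section 11.2.2 already includes patients lost through retreatment for a new infection, so these figures do not change.

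**3. Data lost from PCT and FCT**

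The share with a new infection by Day 42 is an assumption: 5% to 30%, the upper end being the protocol's whole allowance for lost data. Patients lost = 1395 × x, and standard errors grow by a factor of 1/√(1 − x), taking the same x in both arms.

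| x | Patients lost | SE factor |
|---|---|---|
| 5% | 70 | 1.03 |
| 10% | 140 | 1.05 |
| 20% | 279 | 1.12 |
| 30% | 419 | 1.20 |

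With the exclusion limited in time, none of these patients would be lost from PCT or FCT. For Day 14 cure, the needless loss is the part of x that is infected after the Day 14 assessment.

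**4. Supportive ITT analysis at Day 28**

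This illustration assumes true cure of 93% v 95%, new infections after Day 28 in 20% v 10% of cured patients, none among failures, and no missing data.

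- CDA: 0.93×0.80 / (0.93×0.80 + 0.07) = 0.744/0.814 = 91.4%
- Artemether-lumefantrine: 0.95×0.90 / (0.95×0.90 + 0.05) = 0.855/0.905 = 94.5%

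The difference moves from −2.0 to −3.1 points. With 20% in both arms it is 0.744/0.814 − 0.76/0.81 = 91.4% − 93.8% = −2.4 points.

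**5. Uncorrected ACPR**

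In section 6.3.4 the late failure definitions count any parasitaemia, with no PCR condition. Take corrected rates of 93% v 95% and new infections independent of recrudescence. Counted as failures, the uncorrected rate is the corrected rate × (1 − share newly infected). With those patients deleted it stays at 93% v 95%.

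| New infections, CDA v comparator | Counted as failures | Difference | If deleted |
|---|---|---|---|
| 10% v 10% | 83.7% v 85.5% | −1.8 | −2.0 |
| 10% v 5% | 83.7% v 90.3% | −6.6 | −2.0 |
| 20% v 10% | 74.4% v 85.5% | −11.1 | −2.0 |

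**The case against.** The strongest reply is that section 11.3.5.2 is shorthand for section 11.3.5.1. That section derives the Day 28 cure rate without naming a population, and section 11.3.5.7 uses this endpoint in both ITT and per protocol. On that reading, a child reinfected on Day 40 stays in the ITT Day 28 analysis. This is plausible for Day 28 cure, but section 11.3.5.1 sets no such limit for PCT, FCT, densities or ACPR.

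Sections 11.3.2 and 11.3.5.7 also defer dataset and analysis details to the Reporting and Analysis Plan. That plan may well narrow the rule, but the deferral does not withdraw a rule that the protocol states.

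Some stronger inferences are tempting, and the document does not support them:

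- *The non-inferiority conclusion is compromised.* It is not. The primary analysis is per protocol and the unlimited rule is stated for ITT. Section 11.3.3.2 describes comparisons on other secondary endpoints as descriptive.
- *Section 11.3.5.1 is a per-protocol rule that contrasts with an ITT rule.* It is the derivation of the primary endpoint, and it applies wherever that endpoint is analysed.
- *Uncorrected efficacy becomes meaningless or disappears.* Section 11.3.5.7 keeps a per-protocol Day 28 cure rate without PCR correction. Section 11.3.1 also gives the per-protocol population a supportive role for the secondary endpoints. The accurate statement is that uncorrected ACPR in ITT would essentially repeat the corrected figure.

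**Conclusion.** The point holds on the current wording. Section 11.3.5.2 excludes newly infected patients from ITT efficacy analyses without limit. Read with sections 11.3.1 and 6.3.2, it discards complete earlier data, and can discard a known Day 28 outcome, because of a later event. Separately, section 11.3.5.7 conflicts with section 3.2 and the Protocol Summary on whether uncorrected ACPR is analysed at all.

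The sizes are illustrations. The protocol gives no new-infection rate by arm or overall, so the 5% to 30% range behind the 70 to 419 patients and the 3% to 20% growth in standard errors is an assumption. So are the arm-specific shares behind the Day 28 and ACPR examples. The damage is confined to the secondary and supportive ITT analyses.

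**What to change.** In section 11.3.5.2:

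- Limit the exclusion to PCR-corrected endpoints, and only where the new infection occurs on or before that endpoint's assessment day.
- State that PCT, FCT, early parasite densities and time points before the new infection use all ITT patients.
- State that uncorrected ACPR counts a new infection as a failure.

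Then reconcile section 11.3.5.7 with section 3.2 and the Protocol Summary on whether uncorrected ACPR is analysed.

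The cost is a few sentences, to be settled before unblinding. No new data or patients are needed, and the analyses retain more of the data already planned.
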